Isokinetic dynamometry, most commonly performed using systems such as the Biodex, is considered the gold standard for assessing quadriceps and hamstring performance. It provides dynamic, objective, and reproducible measures of torque during concentric and eccentric contractions under controlled angular velocities (**Drouin et al., 2004**). In addition to peak torque, this method yields further performance parameters including total work, power, and fatigue index that offer a comprehensive understanding of muscular capacity (**Impellizzeri & Marcora, 2009**).

A distinct advantage of isokinetic dynamometry lies in its ability to assess the H:Q ratio. The conventional H:Q ratio is defined as the relationship between concentric hamstring and concentric quadriceps peak torque, whereas the functional H:Q ratio compares eccentric hamstring to concentric quadriceps torque (**Aagaard et al., 1998**). These indices are valuable for evaluating muscular balance across the knee joint, informing injury risk assessment,

rehabilitation progress, and return-to-sport readiness (Coombs & Garbutt, 2002).

The validity of isokinetic dynamometry is well established. Torque is measured directly via the device's lever arm at predefined angular velocities, demonstrating strong criterion validity in comparison with other strength assessment methods. Furthermore, the ability to isolate joint movements and regulate contraction speed enhances construct validity, making it particularly suitable for both clinical practice and research applications (Feiring et al., 1990).

Reliability has been consistently confirmed across studies. Test-retest reliability of isokinetic quadriceps and hamstring strength has shown excellent results, with ICCs ranging from 0.85 to 0.99 depending on contraction mode and angular velocity (Maffiuletti et al., 2007; Impellizzeri & Marcora, 2009). H:Q ratio measurements similarly demonstrate strong reproducibility, with ICCs typically reported between 0.82 and 0.95 (Ayala et al., 2012). The standard error of measurement (SEM) for peak torque generally falls between 5–8%, indicating minimal variability due to measurement error (Dirnberger et al., 2012). Moreover, Biodek dynamometers have demonstrated high inter-device reliability, ensuring consistent outcomes across different testing sites (Feiring et al., 1990).

- **Assessment of range of motion ROM:**

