SUBJECTS, MATERIALS AND METHODS

The current study aims to investigate whether incorporating mini squat exercises at different knee flexion angles into a leg press training program enhances hamstring- quadriceps ratio H:Q ratio in football players.

Design of the study:

This study will follow a randomized controlled trial (RCT) design.

Study setting

The study will be conducted at the outpatient physical therapy clinic of Jazan University Hospital, kingdom of Saudi Arbia.

Sample size:

The sample size for this study was determined using G*Power version 3.1.9 (Heinrich-Heine-University, Düsseldorf, Germany). An a priori power analysis was conducted for a repeated measures MANOVA with between-subject factors, setting the alpha level (α) at 0.05, desired power ($1 - \beta$) at 0.80, Pillai's trace (V) at 0.1989, and effect size $f^2(V)$ at 0.2877, targeting isometric muscle strength across four independent groups. The analysis indicated a minimum required sample size of 48 participants, allocating 12 per group. To compensate for possible dropouts, the total sample was increased to 60 participants, with 15 individuals per group (**Wirth et al., 2016**) (figure 3).

[figure not shown]

Fig 3:sample size calculation using G power

Randomization, allocation concealment, and blinding

The enrolled participants will be randomized in a simple randomization way using (www.randomizer.org/links/) by another participant not involved in the data collection. Allocation concealment will be ascertained using sealed, opaque, sequentially numbered envelopes. The participants will be blinded to the assigned intervention group.

Participants

Sixty male football players from Al-Ahli and Al-Ittihad football clubs in the Kingdom of Saudi Arabia. Participants will be asked to sign a written informed consent that includes participation in the experimental trial, permission to use data and/or pictures, and informing them of their right to withdraw at any time (**Appendix I**).

Participants will be randomized into 4 equal groups: an experimental group (A, B, and C), and a Control group (D).

Experimental groups (A, B, and C)

Group A: Fifteen participants will receive mini-squat exercises at 30° knee flexion and leg press exercises

Group B: Fifteen participants will receive mini-squat exercises at 45° knee flexion and leg press exercises

Group C: Fifteen participants will receive mini-squat exercises at 60° and leg press exercises

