Control group D: Fifteen participants will receive leg press exercise program only.

Inclusion criteria:

Participants having the following criteria will be included in the study:

1. Male football players aged between 18–30 years (**Scoz et al., 2021**).
2. Body Mass Index (BMI) between 18.5 and 24.9 kg/m² (**Walsh et al., 2018 & Sattar& Lean, 2009**).
3. Currently training or playing with a registered football club/team.
4. Hamstring-to-Quadriceps (HQ) strength ratio of ≥ 0.6 (**Çelebi et al., 2018**).
5. Having no oral or injectable non-steroidal anti-inflammatory drugs (NSAID), 2 weeks before starting study.
6. Having no oral injectable corticosteroids 3 months before starting the study.

Exclusion criteria:

Participants having any of the following criteria will be excluded from the study:

1. History of acute or chronic injury to the knee, hip, or ankle joint
2. Undergoing any other rehabilitation or physical therapy programs during the six weeks before starting the study
3. Diagnosed with neurological or systemic disorders affecting muscle function or balance

4. Participation in competitive sports or high-intensity training outside the study protocol during the study period
5. Presence of any contraindication to exercise, such as uncontrolled hypertension or heart conditions.
6. Clinically free from lower limb injuries.
7. Having no history of neurological, cardiovascular, or musculoskeletal disorders.

Instrumentation:

a. Isokinetic dynamometry:

Isokinetic dynamometry (**BiodeX System 4 Pro**) is considered the gold standard for assessing muscle strength and HQ ratios, offering valid and reliable measurements through controlled torque assessment during concentric and eccentric contractions. Its criterion validity is well established, and reliability is consistently high, with ICCs ranging from 0.85 to 0.99. Furthermore, its ability to calculate both conventional and functional H:Q ratios provide a reproducible measure of knee muscle balance, making it highly valuable for evaluating injury risk, rehabilitation outcomes, and return-to-sport readiness (**Ayala et al., 2012**) (figure 4).

Fig 4: Isokinetic dynamometry device (BiodeX System 4 Pro, BiodeX Medical Systems, Inc., Shirley, NY, USA) (adopted from Sinacore et al. 2017).

b. leg press machine (FL1801 Isolateral Leg Press):

Fig 5: Leg press machine (FL1801 Isolateral Leg Press, BodyKore Inc., Garden Grove, CA, USA) (adopted from BodyKore Inc., 2025).

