c. Goniometer (Jamar Plus+ Digital 8):

Digital goniometers provide more precise joint range of motion (ROM) measurements than traditional goniometers by offering direct electronic readouts, reducing examiner error. They have demonstrated excellent reliability and validity, with intra-rater ICC values up to 0.96 for knee flexion and 0.92 for extension, and inter-rater ICCs ranging from 0.88 to 0.94. These results highlight their accuracy and reproducibility, making them particularly useful in research and advanced clinical practice (Kolber & Hanney, 2012) (figure 6).

Fig 6: Goniometer (Jamar Plus+ Digital 8" Goniometer, China) (adopted from Jeon et al., 2024).

Assessment procedures:

Participants will be interviewed, and they will be checked for eligibility according to pre-mentioned inclusion criteria. Participants who will be eligible for the study will sign a written consent form, and demographic data regarding height, weight, and BMI will be calculated and recorded. The pretest will be performed 3 days after a familiarization test, which included the same tests in the same order. The same tests will be carried out again 3 days after the last training session.

The assessment procedure will include the following:

1-Measurement of quadriceps strength:

- The participant will be seated on the isokinetic dynamometer chair, with proper posture and alignment ensured.
- The chest, pelvis, thigh, and ankle will be stabilized using adjustable straps to minimize compensatory movements.
- The lateral femoral epicondyle (the anatomical axis of the knee joint) will be aligned with the mechanical axis of the dynamometer arm.
- The lever arm of the dynamometer will be securely attached to the participant's lower leg, just above the ankle, using a padded cuff.

- Test Parameter Settings will be:
 - Mode: Concentric contraction.
 - Velocity: Commonly set at 60°/s for maximal strength.
 - The range of motion (ROM): between 90°knee flexion to full knee extension.
 - Repetitions: 3–5 maximal repetitions.
- The participant will be allowed to perform a submaximal warm-up trial to become familiar with the movement and resistance.
- The participant will be instructed to perform maximal knee extension against the resistance of the device, moving from a flexed to an extended position.
- The test will be conducted unilaterally, assessing one leg at a time.
- The participant will be encouraged to exert maximal effort during each repetition.

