3. Mini-squat session will last 10 minutes. Squat will be performed in a slow and controlled manner (approximately 2 seconds down and 2 seconds up), with short rests of 15–30 seconds allowed every 1–2 minutes as needed. Approximately six minutes of active squatting will be completed per session, with the remaining time allocated for brief rests and transitions (**adapted from Hartmann et al., 2016**) (figure 9).

Fig 9: Mini squat exercise (adopted from Prentice, 2024).

Statistical analysis

All analyses were carried out using IBM SPSS Statistics version 27 (IBM Corp., Chicago, IL, USA).

- Subject characteristics will be analyzed using ANOVA, while the Chi-squared test will be used to compare the distribution of the affected side among the groups
- The Shapiro-Wilk test assessed the normality of the data, followed by Levene's test to verify the homogeneity of variances across groups.
- A mixed MANOVA will be conducted to evaluate the effects of group on the dependent variable(s).
- Post-hoc multiple comparisons were performed with Bonferroni correction to adjust for Type I error.
- Statistical significance was determined at a threshold of $p < 0.05$.

REFERENCES

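### The familiarisation test can supply a second baseline reading of every outcome, but the analysis gives it no role; using it as a covariate is a cheap precision gain of uncertain size, not the repair of an error

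*Combined protocol and SAP*

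**What the plan says.** In Chapter III, Assessment procedures, the baseline schedule reads: "The pretest will be performed 3 days after a familiarization test, which included the same tests in the same order". The follow-up is: "The same tests will be carried out again 3 days after the last training session". Each player is therefore scheduled for the same quadriceps and hamstring tests three times, twice before training and once after it. H:Q is computed from the two peak torques, so each session can yield all three outcomes.

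Chapter III, Statistical analysis, states: "A mixed MANOVA will be conducted to evaluate the effects of group on the dependent variable(s"). Bonferroni-corrected post-hoc comparisons follow. The section names no covariate, lists no time points and does not mention the familiarisation session. Nothing says whether its readings are kept.

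On reliability, Chapter II, section 12, says: "H:Q ratio measurements similarly demonstrate strong reproducibility, with ICCs typically reported between 0.82 and 0.95". For isokinetic torque the same section gives 0.85 to 0.99. Eligibility requires "Hamstring-to-Quadriceps (HQ) strength ratio of ≥ 0.6", without naming the test on which it is judged. The randomisation section does not say whether the envelope is opened before or after either baseline test.

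**The concern.** By the plan's own ICCs a single pretest carries measurement error, most of all for H:Q, the outcome named in the Chapter III aim. A second reading three days earlier carries further information about the same true value. Using it as a covariate sharpens the group comparison without another visit. The trial has 15 players per arm, planned to be enough if 12 remain, and its pairwise comparisons are Bonferroni-corrected, so precision is scarce. If the familiarisation values are not saved at the time, they cannot be recovered.

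**Working it through.** **The plan's own figure.** Chapter III, Sample size, works from "setting the alpha level (α) at 0.05", "desired power ($1 - \beta$) at 0.80" and "trace (V) at 0.1989, and effect size $f^2(V)$ at 0.2877". Treating Pillai's trace as a single-response statistic, f² = V/(1 − V) = 0.1989/0.8011 = 0.2483. With 3 and 44 degrees of freedom and noncentrality 48 × 0.2483 = 11.9, power at 48 players is 0.79995, so the stated 48 reproduces to rounding. Inflating for 20% loss gives 48/0.80 = 60. (The stated 0.2877 does not match that V; it would imply V = 0.2877/1.2877 = 0.2234. This does not affect what follows.)

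**Inputs for the gain.**
- ICC, the correlation between the two baseline tests: 0.82 to 0.95 for H:Q (Chapter II, section 12).
- τ, the correlation between a player's error-free value before and after the six weeks. It is not in the documents; I assume 0.7 to 1.0.
- Equal variances and independent errors at the three tests, so the correlation of post-test with either baseline is r = τ × ICC.

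**Formulas** (post-test variance set to 1).
- ANCOVA on the pretest only: v1 = 1 − r².
- ANCOVA on pretest and familiarisation: v2 = 1 − 2r²/(1 + ICC).
- Change score: vc = 2(1 − r).
- Cost of one more coefficient with 4 groups and 60 players: (60 − 4 − 2)/(60 − 4 − 3) = 54/53, a factor of about 1.019.

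**Example at τ = 0.9.**
- ICC 0.82: r = 0.738, v1 = 0.4554, v2 = 0.4015. Gross fall 1 − 0.4015/0.4554 = 11.8%; net 1 − 0.8817 × 1.019, about 10%.
- ICC 0.95: r = 0.855, v1 = 0.2690, v2 = 0.2502. Gross fall 7.0%; net about 5%.

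**Fall in H:Q residual variance, two baselines against a pretest-only ANCOVA.**

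| τ (assumed) | ICC 0.82, gross | ICC 0.82, net | ICC 0.95, gross | ICC 0.95, net |
|---|---|---|---|---|
| 0.7 | 4.9% | 3% | 2.0% | 0% |
| 0.8 | 7.5% | 6% | 3.5% | 2% |
| 0.9 | 11.8% | 10% | 7.0% | 5% |
| 1.0 | 20.3% | 19% | 23.7% | 22% |

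For torque at τ = 0.9 the gross fall is 11.4% at ICC 0.85 and 1.9% at ICC 0.99. The latter is no more than the extra coefficient costs.

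**Against the analysis actually planned.** If the group-by-time test of the mixed MANOVA is read as a change-score comparison, then at τ = 0.9 vc is 0.524 (ICC 0.82) or 0.290 (ICC 0.95). The two-covariate model saves 1 − 0.4015/0.524 = 23.4%, or 1 − 0.2502/0.290 = 13.7%, gross. Of this, 13.1% or 7.2% comes from using ANCOVA with the pretest alone.

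**What shrinks the gain** (gross, τ = 0.85, ICC 0.82).
- First session with double the error variance (0.36 instead of 0.18): r = 0.697, r² = 0.4858, v1 = 0.5142. Then v2 = 1 − 0.4858 × (1 + 1.18 − 2 × 0.82)/(1.18 − 0.82²) = 0.4832. The fall is 6.0% instead of 9.3%.
- H:Q screen applied to the familiarisation value, with the cut at the mean: simulation gives 6.2% instead of 9.4%.

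**Learning.** In a simulation with the first test 0.3 SD lower and its error variance 30% larger, the estimated effect was 0.59 with either model. Its SD fell from 0.251 to 0.241, a variance fall of 1 − (0.241/0.251)², about 8%.

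**Power.** Take f² = 0.2483 as the effect after pretest adjustment (an assumption), use the gross variance ratios at τ = 0.9 and reduce the residual degrees of freedom. At 60 players power moves from 0.893 to 0.929 (ICC 0.82) or 0.915 (ICC 0.95). At 48 it moves from 0.799 to 0.850 or 0.829.

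**The case against.** A familiarisation session exists to absorb learning before the real baseline. Leaving it out of the analysis is ordinary practice, contradicts nothing in the documents and introduces no bias. That stands, and it is why this is an improvement and not a fault.

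The documents also do not say that the session is scored or its values kept, so the second baseline is available only if someone records it. That stands too, and the fix has to ask for it.

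A noisier first session, or one used for the H:Q screen, gives less. Both are plausible and lower the gain, though in the cases worked above it stays positive before the cost of the extra coefficient. A learning shift common to all players does no harm when the two readings enter as separate terms.

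The change is also more than a wording edit. It replaces the multivariate model on which the sample size rests. Keeping the analysis multivariate would mean six covariates (three outcomes × two readings) in 48 to 60 players.

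A reader might infer that the second reading is worth a definite 7% to 12%. That range is the gross result at a stability of 0.9, which the documents do not supply, and it is measured against a pretest-only ANCOVA, which they do not plan. A reader might also infer that the plan expressly limits itself to one pretest. That is the likely meaning, given that only one session is labelled the pretest, but the Statistical analysis section lists no time points.

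**Conclusion.** The point holds as a cheap improvement. A duplicate pre-training test is scheduled for every player, the analysis gives it no role, and adjusting for it would normally sharpen the group comparison without bias.

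The benefit is probably modest: for H:Q about 10% (ICC 0.82) or 5% (ICC 0.95) of residual variance net at an assumed stability of 0.9, with about 0% to 22% possible over stabilities of 0.7 to 1.0. For torque at the top of its quoted reliability it is close to nil unless stability is very high. These figures rest on the documents' ICCs, an assumed stability, equal variances and independent errors. The larger saving against a change-score analysis depends on reading the mixed MANOVA that way, and about half of it belongs to ANCOVA on the pretest alone. The documents do not support calling the present plan biased or invalid on this account.

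**What to change.** - In Assessment procedures, state that peak torques and H:Q from the familiarisation test are recorded for analysis.
- In the randomisation section, state that the allocation envelope is opened only after both baseline tests.
- In Inclusion criteria, say which test decides the H:Q criterion.
- In Statistical analysis, analyse each post-test outcome by ANCOVA on group, with the pretest and familiarisation values of that outcome as separate covariates. Keep the Bonferroni correction for group comparisons, and say whether it also covers the three outcomes, since the joint multivariate test is dropped.
- In Sample size, acknowledge that the calculation was made for a different model, or redo it for the ANCOVA.

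The cost is one more data column, one degree of freedom per outcome (about 1.9% of variance at 60 players), and replacement of the mixed MANOVA by per-outcome models that no longer match the sample-size calculation. No extra visit is needed, but the recording must be in place before the first familiarisation session.

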Recent studies have highlighted the importance of exercise selection and angle specificity in resistance training, showing that different knee angles result in varied activation patterns in the quadriceps and hamstrings. However, current literature offers limited insight into the effects of integrating mini squat exercises with leg press training on injury prevention and functional outcomes in athletic populations. In particular, there is a lack of literature on how such a combined leg press and mini squat exercise at different angles influences the H:Q ratio, lower limb neuromuscular control, and performance in young male football players. Therefore, the present study aims to examine whether incorporating mini squats performed at varying knee flexion angles into a leg press training program can improve muscle balance and lower limb strength in football players. The findings may provide valuable guidance for physiotherapists, coaches, and sports scientists in developing evidence-based, angle-specific exercise protocols tailored to the functional demands of athletes. (**Watanabe et al., 2020**).

Delimitation:

This study will be delimited to the following:

1. Male football players aged between 18–30 years (**Scoz et al., 2021**).
2. Body Mass Index (BMI) between 18.5 and 24.9 kg/m² (**Walsh et al., 2018 & Sattar & Lean, 2009**).
3. Participants will receive 18 training sessions, conducted three days per week, over six successive weeks

Basic assumptions:

1. Participants understood and followed the given instructions during assessment and treatment procedures.
2. Participants did not receive any additional medical or physical therapy treatment during the study period.

Hypotheses will be:

1. There is no statistically significant difference between adding 30°, 45°, and 60° knee flexion mini-squat exercises to leg press exercise and leg press exercise alone on quadriceps strength in football players.
2. There is no statistically significant difference between adding 30°, 45°, and 60° knee flexion mini-squat exercises to leg press exercise and leg press exercise alone on hamstrings strength in football players.
3. There is no statistically significant difference between adding 30°, 45°, and 60° knee flexion mini-squat exercises to leg press exercise and leg press exercise alone on the hamstrings-to-quadriceps H:Q ratio in football players.

Definitions of terms

Hamstring-to-quadriceps ratio H:Q ratio:

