- The isokinetic device will record key outcome measures including peak torque (Nm), average power, and total work for each repetition. These values will be used to quantify quadriceps strength (figure 7).

2- Measurement of hamstrings muscle strength:

All previously described quadriceps muscle evaluation procedures will be applied for the hamstrings muscle strength test; however, the range of motion will be set from full knee extension, and the participant will be instructed to actively bend the knee against the resistance of the device to 90°.

3-Hamstring to quadriceps H:Q ratio calculation:

H:Q ratio will be calculated by use this formula:

$$H:Q \text{ Ratio} = \left(\frac{\text{Hamstring Peak Torque (Nm)}}{\text{Quadriceps Peak Torque (Nm)}} \right)$$

- Value interpretation:

- < 0.5: hamstring weakness.
- 0.5-0.7: normal range.
- 0.8-1: strong hamstring.

Fig 7: quadriceps and hamstring muscles strength measurement by isokinetic dynamometer device (adopted from Sinacore et al. 2017).

Treatment procedures:

1) Control group D: The participant will receive 18 sessions of leg press exercise using a leg press machine, conducted over a six-week period. Each training session will consist of 7 sets of 10 repetitions, with inter-set rest intervals of 90 seconds (**Wirth et al., 2016 a)** Before starting the leg press program, a standardized warm-up consisted of 5 min of submaximal cycling on an ergometer and 2 to 3 sets of moderate loaded squats with 6 repetitions each.

10 Repetition Max (10RM) Test:

The 10-repetition maximum (10RM) test will be conducted to determine the initial training load as a following:

- The machine will be loaded with a light weight (approximately 25–30% of the participant's body weight).
- The participant will perform 10 repetitions using proper form.
- The weight will be increased gradually (by 5–10 kg) after each successful attempt.
- This process will continue until the participant reaches a weight they can complete for 10 repetitions with good form, but with difficulty during the final 2 reps.
- That weight will be recorded as the participant's 10 Repetition Maximum (10RM).
- Strength training will then begin at 75–85% of the determined 10RM (**Piper et al., 2021**).

Leg Press Exercise:

1. The seat and backrest of the leg press machine will be adjusted to position the participant's hips and knees at approximately 90 degrees of flexion to ensure a comfortable and standardized starting posture.

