2. The participant's feet will be positioned shoulder-width apart on the footplate, with the toes slightly externally rotated and the heels in full contact with the platform.
3. The participant will maintain full contact with the backrest throughout the exercise, with the head and spine supported. The side handles will be grasped to enhance postural stability and balance.

4. The exercise will commence from a flexed knee position, with particular attention given to maintaining proper knee alignment over the feet, avoiding any medial or lateral deviation.
5. The participant will extend the knees and hips to press the platform upward, taking care to avoid full knee lockout at the end of the movement.
6. The platform will then be returned to the initial position in a controlled manner through knee flexion, maintaining proper form throughout the eccentric phase (figure 8).

[figure not shown]

Fig 8: Leg press exercise adopted from (adapted from Martín et al., 2020).

2) Experimental groups: The participant in each subgroup (A, B, and C) will perform the same leg press exercise protocol applied for group D followed by mini squat exercise program with 5 min of submaximal cycling on an ergometer between 2 treatment programs. A total of 18 sessions will be conducted over a six-week period as follows:

1. **Group A:** participants will receive mini-squat program at 30° in addition to leg press program
2. **Group B:** participants will receive mini squat program at 45° in addition to leg press program
3. **Group C:** participants will receive mini-squat at 60° in addition in addition to leg press program

Mini-squat program:

1. Participants will stand barefoot or wear flat training shoes on a stable surface, placing their feet shoulder-width apart with toes slightly pointed outward.
2. A goniometer will be used during the first session to measure the target knee flexion angle (30° for group A, 45° for group B, and 60° for group C) demonstrated once by the examiner on one leg while the participant stands still. This will be followed by passive guidance into the used angles to help the participant recognize the posture and depth, with instructions to remember the sensation for future sessions; goniometer use will be repeated in later sessions only if corrective feedback is required.

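### Groups A–C cycle for 5 minutes between leg press and mini-squat and group D has no matching bout, so contrasts with D test cycling plus mini-squat

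*Combined protocol and SAP*

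**What the plan says.** Under Participants in Chapter III, the comparator is defined as "Control group D: Fifteen participants will receive leg press exercise program only". The details follow under Treatment procedures. Part 1 (Control group D) puts a warm-up before the leg press: "a standardized warm-up consisted of 5 min of submaximal cycling on an ergometer and 2 to 3 sets of moderate loaded squats". Nothing is described for D after the leg press.

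Part 2 (Experimental groups) gives A, B and C the leg press on the same terms as D. In these three arms, however, it is "followed by mini squat exercise program with 5 min of submaximal cycling on an ergometer between 2 treatment programs". On the schedule, part 2 says "A total of 18 sessions will be conducted over a six-week period". The Mini-squat program adds "Mini-squat session will last 10 minutes", of which about six minutes is active squatting.

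Each of the three hypotheses in Chapter I, one per outcome, is a null of this form: "There is no statistically significant difference between adding 30°, 45°, and 60° knee flexion mini-squat exercises to leg press exercise and leg press exercise alone". The one-line definitions of A, B and C under Participants name only mini-squat and leg press. The cycling between the programmes appears only in the treatment details, and the Statistical analysis section does not mention it.

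**The concern.** A contrast with an active control isolates the added component only if everything else is the same in both arms. Here two things are added to the leg press in A–C: a cycling bout and the mini-squat block. The hypotheses name only the second.

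The bout is perfectly aligned with the contrast against D: all A–C players are scheduled for it at each session and no D player is. Covariate adjustment, a different model or a sensitivity analysis on the trial's own data therefore cannot split its contribution from that of the mini-squat. What is at stake is attribution. A difference from D on quadriceps strength, hamstring strength or H:Q ratio would be reported as an effect of mini-squats, when the design supports only a statement about the two components together.

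**Working it through.** The plan gives no figure of its own on this point, and the sample size calculation does not enter into it. The check sets the arms side by side and then counts minutes.

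**Session content by arm, as described**

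| Component | D | A, B, C |
|---|---|---|
| Warm-up: 5 min cycling plus 2 to 3 sets of squats | yes | yes, if part of the same leg press protocol |
| Leg press, 7 sets of 10 | yes | yes |
| 5 min cycling after the leg press | not described | yes |
| 10 min mini-squat session (about 6 min active) | no | yes |

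Two rows separate A–C from D. No row separates A, B and C from one another; only the squat angle does.

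**Inputs.** 18 sessions and 5 min of interval cycling (Experimental groups); 5 min of warm-up cycling (Control group D); 10 min session with about 6 min active (Mini-squat program); 15 players per group (Participants).

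**Interval cycling per A–C player.** 18 × 5 = 90 min.

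**Mini-squat time per A–C player.** Session time 18 × 10 = 180 min; active time 18 × 6 = 108 min.

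**Share of what is added to the leg press.** By session time, 5 / (5 + 10) = 33%. By active time, 90 / (90 + 108) = 90 / 198 = 45%. These are shares of minutes, not of training stimulus.

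**Total cycling, on two readings of the warm-up**

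- A–C also do D's warm-up: 18 × (5 + 5) = 180 min in A–C against 18 × 5 = 90 min in D. This is the likelier reading, because A–C are said to follow D's leg press protocol.
- A–C skip the warm-up: 90 min in each arm, but placed after the leg press in A–C and before it in D, and the warm-up squats would then also differ. The text does not point this way, and it would not make the arms alike.

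**Scale against the rest of the programme.** Leg press: 7 × 10 × 18 = 1,260 repetitions in every arm. Mini-squat: at about 4 s per repetition, 6 × 60 / 4 = 90 per session, or 90 × 18 = 1,620 in total, in A–C only.

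**Cost of matching by lengthening D's sessions.** 15 × 90 min = 1,350 min = 22.5 hours over the trial.

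**The case against.** The strongest reply has four parts.

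1. **It is a warm-up, not training.** The documents use 5 minutes of submaximal cycling only before the leg press and between the two programmes, never as strength work. Next to 1,260 leg press repetitions it may add little to peak torque at 60°/s. This stands as a reason to expect a small bias. It does not show that the bias is nil, and no figure in the documents settles it. The minute shares above should not be read as shares of effect.

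2. **Testing is 3 days after the last session.** This is in Assessment procedures, and it stands: same-day fatigue or warm-up from the cycling cannot affect the post-test. What remains is adaptation over six weeks, or an influence on how the mini-squats are performed.

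3. **The bout is part of delivering the add-on.** With cycling before each programme, the trial could be seen as comparing leg press plus a package with leg press alone. That is a legitimate question, but the hypotheses do not ask it and the group definitions do not declare it. The defence works only if the wording changes.

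4. **The trial's purposes concern angle.** A reader might infer from the asymmetry that the trial cannot answer its own question. The documents do not support that. The three items under Purposes of the study concern differences between adding mini-squats at 30°, 45° and 60°, and all three arms have the same bout. Only the contrasts with D are touched, although those are what the hypotheses state.

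**Conclusion.** The point holds for the comparisons with group D and only for those. As the arms are described, each estimates the combined effect of 90 minutes of interval cycling and the mini-squat programme over 18 sessions. The attribution problem does not depend on how large the cycling effect is, and analysis cannot repair it.

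The size and direction of the bias are unknown. That it is probably small is a judgement from the way the plan uses submaximal cycling, not a result. Two assumptions matter: that nothing matching is intended for D beyond what is written, and, for the totals of 180 against 90 minutes, that A–C also do D's warm-up. A reader who takes the 2:1 ratio as a measure of bias, or as independent of that assumption, goes further than the text allows.

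The change is worth making before recruitment: it is cheap, and the asymmetry cannot be undone afterwards.

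**What to change.** Reconcile the hypotheses in Chapter I, the group definitions under Participants and parts 1 and 2 of Treatment procedures, so that everything apart from the mini-squat block is the same in all four arms. This includes whatever happens in the interval after the leg press; its content is for the investigators to choose. State explicitly that the warm-up applies to all arms, if that is intended. After this, A–C would still do more exercise than D, but the excess would be the mini-squat block, which is the treatment under test.

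The cost is at most about 5 minutes per session for the 15 players in D, or 22.5 hours over the trial, if their sessions are lengthened to match.

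If the arms are not aligned, say in the hypotheses and the conclusion that the add-on tested against D is interval cycling plus mini-squat, and describe A–C in those terms under Participants. That takes only a change of wording, but the trial then makes no claim against D about mini-squats alone.
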